5.2 Database

The database will be developed by the Programming Team at WCTU and all specifications (i.e. database variables, validation checks, screens) will be agreed between the programmer and appropriate study staff.

5.3 Online video platform

An external online video platform will be used for the REGAIN study interventions. This platform will enable live streaming of intervention sessions and the hosting of on-demand, pre-recorded content. A Data Protection Impact Assessment will be completed in order to identify and minimise risks associated with the online platform. The online platform will be GDPR compliant and Organisation for Review of Care and Health Apps (ORCHA) accredited. Any data that is stored, including the participant's email address, will be encrypted in accordance with NHS Digital guidance and storage will be NHS cloud compliant, conform to ISO 9001/27001/27017/27018 standards and meet the G-Cloud (UK Government) standard.

Private groups will be created on the online platform and administrative access to these given only to UHCW/UoW approved staff. Admins will authorise participant's access to the private groups and participants will be asked for their consent to share utilisation metrics with the group admin. Participants may choose to use a nickname on the online platform to remain anonymous to other members.

5.4 One-to-one consultation platform

The UHCW Trust approved patient video-platform will facilitate all one-to-one consultations between the REGAIN practitioner or qualitative interviewer and a study participant. This will include the best practise usual care advice consultation in the control group, the individual assessment component of the REGAIN intervention and the qualitative interviews. This platform will enable secure patient staff video consultations and operates fully in compliance with GDPR, DCB0129 and DCB0160.

5.5 Data storage

All essential documentation and study records will be stored at WCTU in conformance with the applicable regulatory requirements and access to stored information (electronic and paper) will be restricted to authorised personnel. Electronic data will be stored on password protected university computers in a restricted access building. All data will be stored in a designated storage facility within the WCTU.

5.6 Data access and quality assurance

The majority of data will be received directly from participants who will enter their data into the online study database. Following the completion of an expression of interest (EOI) form (which includes an initial eligibility check) participants will be contacted using the contact details that they have provided on the EOI form to confirm eligibility. Participants will complete an online consent form. After the collection of the baseline demographic data for each participant and following randomisation all data will be pseudonymised. Confidentiality will be strictly maintained and names, addresses or personal identifiable information will not be disclosed to anyone other than the staff involved in running the study. All electronic participant-identifiable information will be held on a secure, password-protected database accessible only to essential personnel. Paper forms will be held in secure, locked filing cabinets within a restricted area of WCTU. Participants will be identified by a participant number only on the paper forms. Direct access to source data (online study database) will be available for study-related monitoring or audit by UHCW or WCTU for internal audit or regulatory

authorities. The PI must arrange for retention of study records on site in accordance with GCP and local Trust's policies.

Direct access to source data/documents will be required for study-related monitoring. For quality assurance, the data and results will be statistically checked. A full data management plan will be produced by the study manager and statistician to outline the data monitoring checks required.

5.7 Data Shared with Third Parties

Requests for data sharing will be managed in accordance with University of Warwick SOP 15 Part 3. The datasets generated during and/or analysed during the current study are/will be available upon request after publication of the main study results. The publication of a study protocol, study results and study data will comply with the NIHR standard terms and will follow Warwick SOP 22: Publication & Dissemination.

5.8 Archiving

Study documentation and data will be archived for at least ten years after completion of the study. Study documentation and data held by NHS PIC sites will be stored in line with their local trust policy.

6. STATISTICAL ANALYSIS

6.1 Power and sample size

We have no data on which to base a sample size estimation. There are no normative data for the PROPr quality of life scores in this population and no external indication of what might be a worthwhile benefit from the intervention on quality of life outcomes for this population. American values for the general population in the USA are a mean score of 50 (1-100 scale) with an SD of 10. Whilst not our preferred practice, we will use the approach of looking for a small to moderate standardised mean effect size of 0.3. Allowing for a clustering effect in the intervention arm, we assume that a group size will consist of a maximum of eight patients. Then assuming an intra cluster coefficient of 0.01, 90% power and type I error rate of 5%, with a 10% loss to follow-up, we require 535 participants. This equates to 272 participants in the intervention arm across up to 34 groups and 263 patients in the control arm (control:intervention = 1:1.03), using computations recommended by Moerbeek [43].

6.2 Statistical analysis of efficacy and harms

6.2.1 Statistics and data analysis

A detailed statistical analysis plan will be written and approved by the Data Monitoring Committee (DMC).

Data will be summarised and reported as per CONSORT, using intention-to-treat analyses.

For the primary outcome measures, treatment effects (with 95% Confidence Intervals) will be estimated using hierarchical linear regression models, Both unadjusted and adjusted (for stratification variables and important patient-level covariates) will be presented. We will estimate and adjust for site effects as a random variable in the model. Other secondary outcomes which are

continuous will be analysed in a similar way. Secondary outcomes which are categorical will be analysed using logistic regression models. We will assess compliance using Compliers Average Causal Effect (CACE) analysis. In the case of missing outcome data, we will compute sensitivity analyses using imputation techniques to examine the impact of missingness.

There are no formal interim analyses for this study.

6.2.2 Planned recruitment rate

A minimum recruitment rate of 67 participants per month will be required, based on a recruitment target of 535 participants over 8 months. Patients will be identified from roughly 20 PIC sites in addition to patients identified via self-referrals. The target recruitment rate for the study has been discussed with and agreed by the Trial Management Group (TMG). We are unable to estimate the numbers of self-referrals to the study at this stage. We will have data on proportion of self-referrals after the internal pilot study.

6.3 Subgroup analyses

Pre-specified, exploratory sub-group analysis will include age, need for critical care support, depression, anxiety, PTSD and ethnicity. The sub-group effects will be assessed using regression modelling with the interaction term of sub-group and treatment. As the sub-groups are not powered, the results will be reported using 95% confidence intervals.

6.4 Health economic evaluation

A prospectively planned economic evaluation will be conducted from a NHS and personal social services perspective, according to the recommendations of the NICE reference case [44].

Participants' health service contacts will be recorded at three, six and 12 months, including healthcare, local authority-provided day care and NHS residential services. Time lost from work (paid/unpaid) and patient-borne health costs (e.g. wheelchair by type, home adaptations, feeding aids, walking aids, home-help, support from relatives) will also be recorded, examining a broader social perspective. Participants will be encouraged to use an electronic or paper calendar to help recall this information at follow-up. Healthcare resource use will be costed using most recently available published national reference costs, reflated to a common year [45, 46].

Generic health-related quality-of-life will be assessed at baseline, three, six, and 12 months using the EQ-5D-5L questionnaire. EQ-5D-5L scores will be converted to health status scores using the UK value set recommended by NICE guidance at the time of analysis [47]. Using the trapezoidal rule, the area-under-the-curve of health status scores will be calculated, providing patient-level QALY estimates. Reflecting the one year timeframe, costs and QALYs will be undiscounted.

Mechanisms of missingness of data will be explored and multiple imputation methods will be applied where appropriate to impute missing data. Imputation sets will be used in bivariate analysis of costs and QALYs, using the STATA MI framework. Within-study (12 month) incremental cost per QALY estimates and confidence intervals will be estimated [48-51]. Findings will be analysed and visualised in the cost-effectiveness plane, as cost-effectiveness acceptability curves, net monetary benefit and value of information analysis. At the time of writing no method is available to analyse one-arm clustering within a bivariate regression framework. Ignoring clustering may result in some over-precision of findings if the clustering effect is significant, although have limited scope to systematically bias findings. The importance of clustering will be explored within a hierarchical univariate sensitivity analysis of net monetary benefit (NMB) at varying thresholds of willingness to pay. If incremental costs and benefits are non-convergent within the study follow-up then extrapolated modelling will be considered.

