#### 5.2 Secondary analyses

For the primary outcome, we will also use a linear regression (heteroscedastic) to estimate the treatment effect, without adjustment of any covariates but adjusting the therapist random effects.

All secondary continuous outcomes (including the health economic outcomes, EQ-5D-5L index and VAS scores) will be analysed using the linear regression (heteroscedastic) specified in the primary analysis method, with the same adjustment. An unadjusted analysis will also be conducted for each outcome.

We will assess the impact of compliance on outcomes using a CACE (Compliers average causal effect) analysis for the primary outcome. CACE models evaluate the average effect of the intervention in participants who comply with their allocated treatment. This preserves randomisation groups and eliminates introducing any potential confounders introduced by PP analysis.

For categorical outcomes, odds ratio with 95% CI will be reported. We will also plot the data over time, with the mean and confidence intervals, for some of the secondary outcomes such as the International Physical Activity Questionnaire (IPAQ short-form).

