#### 5.5 Significance levels and adjustments of p-values for multiplicity

Treatment effects will be presented, with appropriate 95% confidence intervals, for both the unadjusted and adjusted analyses. Tests will be two-sided and considered to provide evidence for a significant difference if p-values are less than 0.05 (5% significance level). All analyses will be conducted as ITT unless otherwise specified. No adjustment of p-values in the analysis as there is no multiple comparison in the analyses.

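### The base-case cost-effectiveness analysis leaves out clustering by REGAIN group because no method is said to exist; one does, and if the intracluster correlation is positive the stated uncertainty is too small (minor)

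*Protocol*

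**What the plan says.** Protocol 6.4 sets out a bivariate analysis of costs and QALYs on multiply imputed data. It leads to an incremental cost per QALY with confidence intervals, a cost-effectiveness plane, acceptability curves, net monetary benefit and value of information. Clustering is left out of this base case for one stated reason, that at the time of writing "no method is available to analyse one-arm clustering within a bivariate regression framework".

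The section then states the consequence itself: "Ignoring clustering may result in some over-precision of findings if the clustering effect is significant". It adds that there is little scope for systematic bias, and it plans a univariate hierarchical model of NMB, at several willingness-to-pay thresholds, as a sensitivity analysis.

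Elsewhere the plan builds clustering in. The sample size in Protocol 6.1 is set "Allowing for a clustering effect in the intervention arm". SAP 5.1.1 gives one-arm clustering as the reason for its heteroscedastic model with a random group or therapist effect. SAP 5.2 extends that model: "All secondary continuous outcomes (including the health economic outcomes, EQ-5D-5L index and VAS scores) will be analysed using the linear regression (heteroscedastic"). SAP 2.5.1 says the live exercise groups are discrete and that participants stay in one group for the eight weeks, so a group ID exists for every REGAIN participant who is placed in a group. The SAP does not restate the cost-effectiveness analysis.

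**The concern.** Outcomes of people treated in the same group may be correlated. If they are, an analysis that treats them as independent gives a standard error that is too small. The intervals for incremental cost, QALYs and NMB, the acceptability curve and the value-of-information result all rest on that standard error, so the headline economic result would look more certain than it is.

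The plan makes the analysis that it says may be over-precise its base case, and the only reason given is that nothing better exists. If a valid bivariate method does exist, that reason falls away. QALYs are the area under the EQ-5D-5L curve, and the SAP allows for clustering when it analyses the EQ-5D-5L index, so the clinical and economic analyses would treat the same measure differently.

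**Working it through.** **Inputs**
- Protocol 6.1: 272 intervention participants in up to 34 groups, 263 controls; "we assume that a group size will consist of a maximum of eight patients"; "looking for a small to moderate standardised mean effect size of 0.3"; "assuming an intra cluster coefficient of 0.01, 90% power and type I error rate of 5%, with a 10% loss to follow-up, we require 535".
- SAP 5.5: "Tests will be two-sided and considered to provide evidence for a significant difference if p-values are less than 0.05".
- SAP 2.8: 585 recruited, 15% loss to follow-up.
- Not in the documents: the ICC for cost, QALY or NMB. Assumed range 0.01 to 0.20, where 0.01 is the sample-size value.

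**Step 1. Reproduce the 535.** Design effect in the intervention arm: DE = 1 + (m − 1) × ICC = 1 + 7 × 0.01 = 1.07. Optimal allocation ratio: k = √1.07 = 1.034.

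Controls = (1.960 + 1.282)² × (1 + DE/k) / 0.3² = 116.75 × 2.0344 = 237.5. Intervention = 1.034 × 237.5 = 245.7. Total 483.2, and 483.2/0.9 = 536.9.

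With m = 8 × 0.9 = 7.2 after losses, the total is 534.8, which rounds up to 535. Without clustering it is 234 per arm, or 468/0.9 = 520. The stated figure reproduces, and one-arm clustering accounts for 535 − 520 = 15 participants.

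**Step 2. Size of the error if clustering is omitted.** With true over unadjusted standard error R:

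R = √{[(1 + 7 × ICC)/272 + 1/263] / [1/272 + 1/263]} = √(1 + 0.4916 × 7 × ICC), because 263/535 = 0.4916.

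The unadjusted SE is too small by 1 − 1/R. A nominal 95% interval covers 2Φ(1.96/R) − 1. An acceptability probability of 0.90 becomes Φ(1.2816/R).

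Example, ICC 0.05: R = √(1 + 0.4916 × 0.35) = √1.1721 = 1.083; 1 − 1/1.083 = 7.6%; 1.96/1.083 = 1.810, coverage 93.0%; 1.2816/1.083 = 1.184, probability 0.882.

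| ICC | DE | R | True SE larger by | Unadjusted SE too small by | Coverage of nominal 95% CI | 0.90 becomes |
|---|---|---|---|---|---|---|
| 0.01 | 1.07 | 1.017 | 1.7% | 1.7% | 94.6% | 0.896 |
| 0.05 | 1.35 | 1.083 | 8.3% | 7.6% | 93.0% | 0.882 |
| 0.10 | 1.70 | 1.159 | 15.9% | 13.7% | 90.9% | 0.866 |
| 0.20 | 2.40 | 1.299 | 29.9% | 23.0% | 86.9% | 0.838 |

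At 585 recruited with 15% loss, same allocation and groups of 8, R is unchanged to two decimals (1.017, 1.083 and 1.160 at the first three ICCs). If losses shrink groups to 7.2, R is about 1.015, 1.07, 1.14 and 1.27.

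**Step 3. Is there a method?** Fit the two equations (cost and QALY on arm). In the REGAIN arm, sum each pair of residuals within group before forming the covariance matrix; in the control arm, treat each person as a cluster of one. The result is a 2 × 2 covariance matrix for incremental cost and incremental QALY, from which NMB intervals and the acceptability curve follow.

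A simulation of 34 groups of 8 against 263 controls was run 4,000 times per ICC. It used bivariate normal data with assumed values (QALY SD 0.15, cost SD 2,500, correlation −0.2, threshold 20,000). Coverage of the nominal 95% NMB interval was:

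| ICC | Unadjusted | Cluster-robust bivariate |
|---|---|---|
| 0 | 94.1% | 93.9% |
| 0.01 | 94.8% | 95.0% |
| 0.05 | 92.6% | 94.6% |
| 0.10 | 90.7% | 95.1% |

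The Monte Carlo standard error is √(0.95 × 0.05/4,000) = 0.34 percentage points. The ICC 0 row is about one point low for both methods, so differences of that order should not be read closely. At ICC 0.10 the mean unadjusted SE was 369 against an empirical SD of 427; the mean cluster-robust SE was 427. A repeat simulation gave 94.8% and 94.6% cluster-robust against 93.1% and 90.7% unadjusted at ICC 0.05 and 0.10. Neither run is taken to test imputation; the one tabulated had no missing data.

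**The case against.** The strongest reply is that Protocol 6.4 already deals with this. It names the risk in conditional terms and plans a hierarchical NMB analysis. An acceptability curve is the probability that NMB exceeds zero at each threshold, so that analysis can give clustering-adjusted intervals and an adjusted curve. At the only ICC in the documents the effect is 1.7% of the standard error, and 0.90 moves to 0.896. Eight is the stated maximum group size, so for group-level clustering the ratios are upper bounds at each ICC. On this view all that is left is which planned analysis is called the base case.

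Most of this stands, and it is why the point is minor. It does not rescue the stated reason: a valid bivariate analysis exists and uses an identifier that the primary clinical model already needs. The sentence might be meant narrowly, about a bivariate random-effects model, but cluster-robust covariance or a bootstrap needs no such model.

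Some stronger readings are tempting, and the documents do not support them:
- *The intervals are certain to be too narrow, or the plan admits that they are.* Both depend on a positive ICC, and the Protocol says only that over-precision may arise.
- *The economic evaluation ignores clustering altogether.* It has a planned sensitivity analysis.
- *The ICC for cost must be well above 0.01 because session costs are shared among attenders.* No costing rule of that kind is given. With a fixed cost per session attended, this group component need not arise.
- *The point estimates are biased.* Nothing here shows that.
- *The SAP and Protocol contradict each other on EQ-5D-5L.* They differ in approach, but SAP 5.1.1 also drops the random effect if group and centre effects are negligible, so the clinical allowance is itself conditional.

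**Conclusion.** The concern holds as a minor point. The premise that no method is available is wrong, and with it goes the only stated reason for an unclustered base case. If the ICC is positive, base-case intervals are too narrow and acceptability probabilities are pushed away from 0.5. The effect is small at ICC 0.01 and becomes material only at values such as 0.05 to 0.20, which are an assumed range and not a forecast.

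The figures assume groups of 8, the planned arm sizes, equal within-arm variances and clustering by group only. SAP 5.1.1 leaves open whether the random effect is for group or therapist; clustering by therapist is not covered by the table. The simulation's SDs, correlation and threshold are also assumptions.

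**What to change.** In Protocol 6.4, or wherever the economic analysis is finally specified:

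1. Delete the statement that no method is available.
2. Make the clustered analysis the base case. In each imputed dataset, fit the bivariate cost and QALY regression with cluster-robust covariance (REGAIN group ID; a separate ID for each control), or bootstrap it by resampling groups in the REGAIN arm and individuals in the control arm, then pool. Alternatively, promote the planned hierarchical NMB model to base case for the intervals and acceptability curve.
3. Make the imputation model compatible with the group structure in the REGAIN arm. Adding clustering only at the analysis step would leave the imputed values without it.
4. Report the ICCs for cost, QALY and NMB.
5. Keep the unclustered bivariate model as the sensitivity analysis.

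No new data are needed, since the clinical model already requires the group ID. The cost is slightly wider intervals and a little more analysis work, mostly in the imputation. If the ICC proves negligible, the two analyses will nearly agree and little is lost.

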6.5 Qualitative data analysis

The semi-structured interviews with ~n=25 intervention group, ~n=25 control and ~n=5 practitioner's will be digitally recorded, subject to the permission of each participant/practitioner, pseudonymised, and transcribed verbatim. Framework analysis will be used to analyse the data [52]. This will involve:

- Data familiarisation: listening to digital recordings, reading transcripts, and re-reading field notes;
- Identifying a thematic framework: key issues and themes identified and an index of codes is developed;
- Indexing: this index is applied to all data;
- Charting: a summary of each passage of text is transferred into a chart to allow more overall and abstract consideration of index codes across the data set and by each individual;
- Mapping and interpretation: understanding the meaning of key themes, dimensions and broad overall picture of the data and identifying and understanding the typical associations between themes and dimensions. We will remain vigilant for any new themes emerging from the data as we progress. The computer package NVivo 12 will be used to organise the data.

The charting process provides an opportunity to code data from numerous perspectives. The computer package NVivo 11 will be used to organise the analysis.

The findings of the qualitative work will be reported as a separate chapter in the final report but will also be incorporated in the discussion to bring together a synthesis of all the results, thus helping to explore and explain the overall 'value' of the interventions. Quantitative and qualitative data will be integrated using a mixed methods matrix' where quantitative responses can be compared to interview data and recorded on a matrix. This is particularly useful to reveal gaps between quantitative and qualitative insights.

From the intervention delivery recordings (initial practitioner assessment, the exercise familiarisation session and the psychological support sessions) and control (1:1 session) recordings, a purposively selected subset (10%) of recordings will be analysed, with a checklist to assess fidelity and using the qualitative approach detailed above to help understand which areas generated discussion and what issues were discussed. Intervention fidelity will be assessed using the tenets highlighted by Mars et al.

